# 10.6. Appendix 6: Division of AIDS (DAIDS) Table for Grading the Severity of Adult and Pediatric Adverse Events

## 10.6.1. Laboratory Values

Laboratory abnormalities will be graded according to the DAIDS grading table Version 2.1, July 2017. Laboratory results are converted to use SI units; only the numeric part of the criteria will be used. If for a laboratory parameter there are multiple grades sharing the same criteria, the maximum grade will be used.

HEMATOLOGY				
	Grade 1	Grade 2	Grade 3	Grade 4
Absolute Lymphocyte Count, Low (cell/mm³; cells/L) > 5 years of age (not HIV infected)	600 to < 650 0.600 × 10  to < 0.650 × 10 	500 to < 600 0.500 × 10  to < 0.600 × 10 	350 to < 500 0.350 × 10  to < 0.500 × 10 	< 350 < 0.350 × 10 
Absolute Neutrophil Count, Low (cells/mm³; cells/L) > 7 days of age	800 to 1,000 0.800 × 10  to 1.000 × 10 	600 to 799 0.600 × 10  to 0.799 × 10 	400 to 599 0.400 × 10  to 0.599 × 10 	< 400 < 0.400 × 10 
Hemoglobin, Low (g/dL; mmol/L)	10.0 to 10.9	9.0 to < 10.0	7.0 to < 9.0	< 7.0
≥ 13 years of age (male only)	6.19 to 6.76	5.57 to < 6.19	4.34 to < 5.57	<4.34
Hemoglobin, Low (g/dL; mmol/L)	9.5 to 10.4	8.5 to < 9.5	6.5 to < 8.5	< 6.5
≥ 13 years of age (female only)	5.88 to 6.48	5.25 to < 5.88	4.03 to < 5.25	< 4.03
Platelets, Decreased (cells/mm³; cells/L)	100,000 to < 125,000 100.000 × 10  to < 125.000 × 10 	50,000 to < 100,000 50.000 × 10  to < 100.000 × 10 	25,000 to < 50,000 25.000 × 10  to < 50.000 × 10 	< 25,000 < 25.000 × 10 
White Blood Cell, Decreased (cells/mm³; cells/L) > 7 days of age	2,000 to 2,499 2.000 × 10  to 2.499 × 10 	1,500 to 1,999 1.500 × 10  to 1.999 × 10 	1,000 to 1,499 1.000 × 10  to 1.499 × 10 	< 1,000 < 1.000 × 10 

Clinical Chemistry				
	Grade 1	Grade 2	Grade 3	Grade 4
Albumin Low (ald : all )	3.0 to < LLN	≥ 2.0 to < 3.0	< 2.0	NA
Albumin, Low (g/dL; g/L)	30 to < LLN	≥ 20 to < 30	< 20	NA

Clinical Chemistry				
	Grade 1	Grade 2	Grade 3	Grade 4
Alkaline Phosphatase, High	1.25 to < 2.5 × ULN	2.5 to < 5.0 × ULN	5.0 to < 10.0 × ULN	≥ 10.0 × ULN
Alanine Aminotransferase, High	1.25 to < 2.5 × ULN	2.5 to < 5.0 × ULN	5.0 to < 10.0 × ULN	≥ 10.0 ULN
Amylase (Total), High	1.1 to < 1.5 × ULN	1.5 to < 3.0 × ULN	3.0 to < 5.0 × ULN	≥ 5.0 × ULN
Aspartate Aminotransferase, High	1.25 to < 2.5 × ULN	2.5 to < 5.0 × ULN	5.0 to < 10.0 × ULN	≥ 10.0 × ULN
Bicarbonate, Low (mEq/L; mmol/L)	16.0 to < LLN 16.0 to < LLN	11.0 to < 16.0 11.0 to < 16.0	8.0 to < 11.0 8.0 to < 110.	< 8.0 < 8.0
Direct Bilirubin, High > 28 days of age	NA	NA	> ULN with other signs and symptoms of hepatotoxicity	> ULN with life-threatening consequences (e.g., signs and symptoms of liver failure)
Total Bilirubin, High > 28 days of age	1.1 to < 1.6 × ULN	1.6 to < 2.6 × ULN	2.6 to < 5.0 × ULN	≥ 5.0 × ULN
Calcium, High (mg/dL; mmol/L)	10.6 to < 11.5	11.5 to < 12.5	12.5 to < 13.5	≥ 13.5
≥ 7 days of age	2.65 to < 2.88	2.88 to < 3.13	3.13 to < 3.38	≥ 3.38
Calcium, Low (mg/dL; mmol/L)	7.8 to < 8.4	7.0 to < 7.8	6.1 to < 7.0	< 6.1
≥ 7 days of age	1.95 to < 2.10	1.75 to < 1.95	1.53 to < 1.75	< 1.53
Creatine Kinase, High	3 to < 6 × ULN	6 to < 10 × ULN	10 to < 20 × ULN	≥ 20 × ULN
Creatinine, High Choose the method that selects for the higher grade	1.1 to 1.3 × ULN	> 1.3 to 1.8 × ULN OR Increase to 1.3 to < 1.5 × participant's baseline	> 1.8 to < 3.5 ULN OR Increase to 1.5 to < 2.0 × participant's baseline	≥ 3.5 × ULN OR Increase of ≥ 2.0 × participant's baseline
Glucose Fasting, High (mg/dL; mmol/L)	110 to 125 6.11 to < 6.95	> 125 to 250 6.95 to < 13.89	> 250 to 500 13.89 to < 27.75	≥ 500 ≥ 27.75
Glucose, Low (mg/dL; mmol/L) ≥ 1 month of age	55 to 64 3.05 to < 3.55	40 to < 55 2.22 to < 3.05	30 to < 40 1.67 to < 2.22	< 30 < 1.67
Lipase, High	1.1 to < 1.5 × ULN	1.5 to < 3.0 × ULN	3.0 to < 5.0 × ULN	≥ 5.0 × ULN
Cholesterol, Fasting, High (mg/dL; mmol/L) ≥ 18 years of age	200 to < 240 5.18 to < 6.19	240 to < 300 6.19 to < 7.77	≥ 300 ≥ 7.77	NA
Triglycerides, Fasting, High (mg/dL; mmol/L)	150 to 300 1.71 to 3.42	> 300 to 500 > 3.42 to 5.7	> 500 to < 1.000 > 5.7 to 11.4	> 1,000 > 11.4
Phosphate, Low (mg/dL; mmol/L) > 14 years of age	2.0 to < LLN 0.65 to < LLN	1.4 to < 2.0 0.45 to < 0.65	1.0 to < 1.4 0.32 to < 0.45	< 1.0 < 0.32
Potassium, High (mEq/L; mmol/L)	5.6 to < 6.0 5.6 to < 6.0	6.0 to < 6.5 6.0 to < 6.5	6.5 to < 7.0 6.5 to < 7.0	≥ 7.0 ≥ 7.0

Clinical Chemistry				
	Grade 1	Grade 2	Grade 3	Grade 4
Potossium Low (mEa/L: mmol/L)	3.0 to < 3.4	2.5 to < 3.0	2.0 to < 2.5	< 2.0
Potassium, Low (mEq/L; mmol/L)	3.0 to < 3.4	2.5 to < 3.0	2.0 to < 2.5	< 2.0
Codina High (mFa/L)	146 to < 150	150 to < 154	154 to < 160	≥ 160
Sodium, High (mEq/L; mmol/L)	146 to < 150	150 to < 154	154 to < 160	≥ 160
Codium Lourine Fall Lourine (III)	130 to < 135	125 to < 130	121 to < 125	≤ 120
Sodium, Low (mEq/L; mmol/L)	130 to < 135	125 to < 130	121 to < 125	≤ 120
Usia Aaid High (mEa/L, mmal/L)	7.5 to < 10.0	10.0 to < 12.0	12.0 to < 15.0	≥ 15.0
Uric Acid, High (mEq/L; mmol/L)	0.45 to < 0.59	0.59 to < 0.71	0.71 to < 0.89	≥ 0.89

NA=not applicable; LLN = lower limit of normal; ULN=upper limit of normal.

Urinalysis				
	Grade 1	Grade 2	Grade 3	Grade 4
Glucose/Glycosuria (random collection tested by dipstick)	Trace to 1+ or ≤ 250 mg	2+ or > 250 to ≤ 500 mg	> 2+ or > 500 mg	NA
Protein/Proteinuria (random collection tested by dipstick)	1+	2+	3+ or higher	NA
Red Blood Cells (RBCs)/Hematuria (not to be reported based on dipstick findings or on blood believed to be of menstrual origin)	6 to < 10 RBCs per high power field	≥ 10 RBCs per high power field	Gross, with or without clots OR with RBC casts OR intervention indicated	Life-threatening consequences

NA=not applicable

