# **10.2.** Appendix 2: Clinical Laboratory Tests

- The tests detailed in Table 2 will be performed by the local laboratory.
- Protocol-specific requirements for inclusion or exclusion of participants are detailed in Section 5 of the protocol.
- Additional tests may be performed at any time during the study as determined necessary by the investigator or required by local regulations.
- Pregnancy Testing
  - Refer to Section 5.1 Inclusion Criteria for screening pregnancy criteria.
  - Pregnancy testing (urine or serum as required by local regulations) should be conducted at the time points indicated in the SoA (Section 1.3).
  - Additional serum or urine pregnancy tests may be performed, as determined necessary by the investigator or required by local regulation, to establish the absence of pregnancy at any time during the participant's participation in the study.

Laboratory Assessments	Parameters			
Hematology	Platelet Count Red Blood Cell Count Hemoglobin Hematocrit	Red Blood Cell Indices: Mean corpuscular volume Mean corpuscular hemoglobin	White blood cell count with differential:NeutrophilsLymphocytesMonocytesEosinophilsBasophils	
Clinical Chemistry ¹	Blood urea nitrogen	Aspartate aminotransferase	Globulin	
	Creatinine	Alanine aminotransferase	Anion gap	
	Glucose (fasting) Potassium	Gamma-glutamyl transferase Total and direct bilirubin	Alkaline phosphatase Uric acid	
	Sodium	Lactate dehydrogenase	Creatine phosphokinase	
	Calcium	Total cholesterol	Serum lipase	
	Chloride	Triglycerides	Serum amylase	
	Phosphorus	Total protein		
	Carbon dioxide	Albumin		
Routine Urinalysis	
 
Specific gravity
 
pH, glucose, protein, blood, ketones, bilirubin, urobilinogen, nitrite, and leukocyte esterase by dipstick
 
Microscopic examination (if blood, leukocyte esterase, or protein is abnormal)
 
			

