### 5.2. Baseline Definitions

For all endpoints (except as noted in baseline definitions), the baseline value will be the latest pre-dose assessment with a non-missing value, including those from unscheduled visits. If time is not collected, Day 1 assessments are assumed to be taken prior to first dose and used as baseline. Baseline is applied to each treatment period.

Parameter	Study As	sessment Basel	s Considered as ine	Baseline Used in Data Display					
	Screening	Day -1	Day 1 (Pre-Dose)	Period 1 Period 2					
Safety									
Vital Sign	Х	Х	X	Day 1 (Pre-Dose) for each period					
12-Lead ECG	Х	Χ	Х	Day 1 (Pre-Dose)[1] for each period					
Hematology	Х	Х		Day -1 Period 1 Day 14					
Clinical Chemistry	Х	Х		Day -1 Period 1 Day 14					
Urinalysis	Х	Χ		Day -1	Period 1 Day 14				

 The average (for quantitative assessments) or the worst case (for interpretation) of the predose triplicate assessments on Day 1 of Period 1 will be used as the baseline for Period 1. The average (for quantitative assessments) or the worst case (for interpretation) of the predose triplicate assessments on Day 1 of Period 2 will be used as the baseline for Period 2.

Unless otherwise stated, if baseline data is missing no derivation will be performed and baseline will be set to missing.

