## 10.9.5. Safety Tables

Safety:	Tables				
No.	Population	IDSL / Example Shell	Title	Programming Notes	Deliverable [Priority]
Advers	e Events (AEs)			•	
2.1.	Safety	AE1CP	Summary of Adverse Events by System Organ Class and Preferred Term		SAC
2.2.	Safety	AE1CP	Summary of Drug-Related Adverse Events by System Organ Class and Preferred Term		SAC
2.3.	Safety	AE3	Summary of Common (>=5%) Adverse Events by Overall Frequency		SAC
2.4.	Safety	AE15	Summary of Common (>=5%) Non-serious Adverse Events by System Organ Class and Preferred Term (Number of Subjects and Occurrences)		SAC
2.5.	Safety	AE16	Summary of Serious Adverse Events by System Organ Class and Preferred Term (Number of Subjects and Occurrences)		SAC
2.6.	Safety	AE5A	Summary of Adverse Events by System Organ Class and Preferred Term and Maximum Intensity		SAC
Labora	tory: Chemistry	/			•
2.7.	Safety	LB1	Summary of Clinical Chemistry Changes from Baseline		SAC
2.8.	Safety	LB16	Summary of Clinical Chemistry Results by Maximum Grade Increase Post-Baseline Relative to Baseline		SAC
Labora	tory: Hematolo	gy		•	
2.9.	Safety	LB1	Summary of Hematology Changes from Baseline		SAC
2.10.	Safety	LB16	Summary of Hematology Results by Maximum Grade Increase Post-Baseline Relative to Baseline		SAC

Safety: Tables						
No.	Population	IDSL / Example Shell	Title	Programming Notes	Deliverable [Priority]	
Labora	tory: Urinalysis	,				
2.11.	Safety	UR3	Summary of Urinalysis Dipstick Results		SAC	
2.12.	Safety	LB1	Summary of Urine Concentration Changes from Baseline		SAC	
2.13.	Safety	LB16	Summary of Urinalysis by Maximum Grade Increase Post- Baseline Relative to Baseline		SAC	
ECG						
2.14.	Safety	EG1	Summary of ECG Findings		SAC	
2.15.	Safety	EG2	Summary of ECG Changes from Baseline		SAC	
2.16.	Safety	EG10	Summary of Maximum QTc Values Post-Baseline Relative to Baseline by Category		SAC	
2.17.	Safety	EG11	Summary of Maximum Increase in QTc Values Post-Baseline Relative to Baseline by Category		SAC	
Vital Si	gns					
2.18.	Safety	VS1	Summary of Vital Sign Changes from Baseline		SAC	
C-SSR	S					
2.19.	Safety	CSSRS4	Listing of C-SSRS Suicidal Ideation and Behavior Data	Only include participants who have suicidal ideation or behavior	SAC	

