## 10.9.9. ICH Listings

ICH: Li	stings				
No.	Population	IDSL / Example Shell	Title	Programming Notes	Deliverable [Priority]
Subjec	t Disposition			•	·
1.	Safety	ES3	Listing of Reasons for Study Withdrawal		SAC
2.	Screened	DS7	Listing of Reasons for Screen Failure		SAC
Protoc	ol Deviations				·
3.	Safety	DV2	Listing of Important Protocol Deviations		SAC
4.	Safety	IE3	Listing of Subjects with Inclusion/Exclusion Criteria Deviations		SAC
Popula	tions Analysed				.
5.	Safety	SP3A	Listing of Subjects Excluded from Any Population		SAC
Demog	raphic and Bas	eline Characteris	tics		
6.	Safety	DM2	Listing of Demographic Characteristics		SAC
7.	Safety	DM9	Listing of Race		SAC
Prior a	nd Concomitan	t Medications			·
8.	Safety	CM5	Listing of Concomitant Medications	Based on GSK Drug Dictionary	SAC
Exposi	ire and Treatmo	ent Compliance			·
9.	Safety	EX4	Listing of Exposure Data		SAC
10.	Safety	POP_L1	Listing of Meal Data		SAC
Advers	e Events				
11.	Safety	AE2	Listing of Relationship Between System Organ Class and Verbatim Text		SAC
12.	Safety	AE7	Listing of Subject Numbers for Individual Adverse Events		SAC

ICH: Li	stings				
No.	Population	IDSL / Example Shell	Title	Programming Notes	Deliverable [Priority]
13.	Safety	AE9CP	Listing of All Adverse Events		SAC
Serious	s and Other Sig	nificant Adverse	Events		·
14.	Safety	AE9CP	Listing of Study Drug Related Adverse Events		SAC
15.	Safety	AE9CP	Listing of Serious Adverse Events (Fatal & Non-Fatal)		SAC
16.	Safety	AE14	Listing of Reasons for Considering as a Serious Adverse Event		SAC
17.	Safety	AE9CP	Listing of Adverse Events Leading to Withdrawal from Study		SAC
Hepato	biliary (Liver)				
18.	Safety	MH2	Listing of Medical Conditions for Subjects with Liver Stopping Events		SAC
19.	Safety	SU2	Listing of Substance Use for Subjects with Liver Stopping Events		SAC
All Lab	oratory				
20.	Safety	LB5A	Listing of Clinical Chemistry with any Toxicities		SAC
21.	Safety	LB5A	Listing of All Clinical Chemistry Data for Subjects with any Toxicities		SAC
22.	Safety	LB5A	Listing of Hematology with any Toxicities		SAC
23.	Safety	LB5A	Listing of All Hematology Data for Subjects with any Toxicities		SAC
24.	Safety	LB5A	Listing of Urinalysis with any Toxicities		SAC
25.	Safety	LB5A	Listing of All Urinalysis Data for Subjects with any Toxicities		SAC
ECG					
26.	Safety	EG6	Listing of All ECG Findings		SAC
27.	Safety	EG6	Listing of All Abnormal ECG Findings		SAC
28.	Safety	EG4	Listing of All ECG Values		SAC

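### The SAP's laboratory-grading rule turns every direct bilirubin above ULN into Grade 4 and makes Grade 3 impossible, against the table's own definitions

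*SAP*

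**What the plan says.** SAP 10.6.1 (Laboratory Values) grades laboratory abnormalities by the DAIDS table and sets two programming rules. The first is that "only the numeric part of the criteria will be used". The second settles ties: "If for a laboratory parameter there are multiple grades sharing the same criteria, the maximum grade will be used".

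In the clinical chemistry table that follows, the direct bilirubin row has no Grade 1 or 2. Grade 3 reads "> ULN with other signs and symptoms of hepatotoxicity". Grade 4 reads "> ULN with life-threatening consequences (e.g., signs and symptoms of liver failure").

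Protocol Appendix 2, Table 2 includes "Total and direct bilirubin" in the required chemistry panel. The derived grades are used in SAP Table 2.8, "Summary of Clinical Chemistry Results by Maximum Grade Increase Post-Baseline Relative to Baseline", and in Listing 20, "Listing of Clinical Chemistry with any Toxicities", with its companion Listing 21. SAP 5.2 says "Baseline is applied to each treatment period"; for chemistry that is Day -1 for Period 1 and Period 1 Day 14 for Period 2. The SAP contains no exception or footnote for direct bilirubin.

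**The concern.** For direct bilirubin the clinical text is the only thing that separates Grade 3 from Grade 4, and either of them from no grade at all. A rule that discards that text and resolves the tie upward gives the most severe grade to any value above ULN.

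Change in clinical laboratory results is part of the secondary safety endpoint. The report could therefore show Grade 4 chemistry in healthy volunteers who had none of the consequences that define that grade. Protocol 7.1.4 also lists Grade 4 laboratory abnormalities among the individual stopping criteria and exempts only asymptomatic cholesterol, triglyceride and CPK increases. The SAP rule does not trigger stopping. However, a programmed Grade 4 in a participant who continued dosing could look afterwards like a stopping event that nobody acted on.

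**Working it through.** **Step 1: apply the rule to the row.**

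| Grade | Criterion, shortened | Numeric part |
|---|---|---|
| 1 | not applicable | none |
| 2 | not applicable | none |
| 3 | > ULN plus signs or symptoms of hepatotoxicity | > ULN |
| 4 | > ULN plus life-threatening consequences | > ULN |

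Grades 3 and 4 have the same numeric part, so the tie rule returns 4. Coding the rule for values from 0 to 20 × ULN in steps of 0.01 (2001 values) gives 101 ungraded (all ≤ 1.00 × ULN), 1900 at Grade 4 and none at Grades 1, 2 or 3.

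**Step 2: compare with total bilirubin in the same table.** Its limits start at 1.1, 1.6, 2.6 and 5.0 × ULN for Grades 1 to 4. At 1.01 × ULN total bilirubin is ungraded and direct bilirubin is Grade 4. At 2 × ULN they are Grade 2 and Grade 4.

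**Step 3: is this row alone affected?** The tables have 32 rows (6 hematology, 23 chemistry, 3 urinalysis). Direct bilirubin is the only row in which two grades share an actual numeric criterion. Hematuria Grades 3 and 4 have no numeric part, so no value can trigger either.

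**Step 4: how often might it show?** The documents give no rate of direct bilirubin above ULN, so the proportion *p* of values above ULN is assumed to be 1%, 2.5% or 5%. The other inputs are 16 treated participants (protocol 9.2.2) and six chemistry draws each after Screening (protocol 1.3): Day -1; Period 1 Days 7 and 14; Period 2 Days 3, 7 and 9.

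For a single visit, P(at least one of 16) = 1 − (1 − p)^16:
- 1 − 0.99^16 = 0.149
- 1 − 0.975^16 = 0.333
- 1 − 0.95^16 = 0.560

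Over repeated draws, exceedance is modelled as a latent normal variable above its 1 − p quantile, with the same correlation ρ between any two draws in a person.
- *Listings event:* any of the five post-baseline draws is above ULN.
- *Table 2.8 event:* Day -1 is not above ULN and Period 1 Day 7 or 14 is; or Period 1 Day 14 is not above ULN and Period 2 Day 3, 7 or 9 is.

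If π is the per-participant probability of the event, the chance of at least one is 1 − (1 − π)^16. For example, at p = 2.5% and ρ = 0.8, π = 0.0637 for the listings and 0.0518 for Table 2.8, giving 0.651 and 0.573.

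| Output | ρ | p = 1% | p = 2.5% | p = 5% |
|---|---|---|---|---|
| Listings 20–21 | 0 | 55% | 87% | 98% |
| | 0.8 | 37% | 65% | 86% |
| | 1 | 15% | 33% | 56% |
| Table 2.8 | 0 | 55% | 87% | 98% |
| | 0.8 | 32% | 57% | 78% |
| | 1 | 0% | 0% | 0% |

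The zeros at ρ = 1 arise because anyone above ULN is then already above it at baseline and shows no rise; such a participant still appears in the listings. The expected number of participants with a false rise in Table 2.8 at ρ = 0.8 is 16π = 0.38, 0.83 and 1.44.

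**The case against.** The strongest reply is that this is a disclosed, conservative convention. The SAP states both rules just above the table. Since direct bilirubin is the only row on which the tie rule acts, the sentence may have been written for it. That may be so, but the SAP gives no reason and does not mark the resulting grades as numeric-only. Nor is the result a cautious choice between neighbouring grades, because an isolated value above ULN has no grade under the full criteria.

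One could also argue that > ULN is not numeric, which would leave the row ungraded. Other rows use ULN as a numeric bound, and on that reading the tie rule would have no row to act on. If the sponsor does read it that way, the text still needs clarifying.

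The frequency is a fair point. The volunteers are screened for liver disease and raised bilirubin, and 1% is not a documented floor. At an equally unsupported 0.1%, the chance for Table 2.8 falls to 7.7% (ρ = 0) or 4.7% (ρ = 0.8); at 0.25% it is 18% or 11%. The probabilities are illustrations. The misgrading itself is certain whenever a value exceeds ULN. The listing figures count only post-baseline draws, although the listing title has no such limit, so they may be low for a given p.

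The table and listing shells are not in the documents, so the exact layout of Table 2.8 cannot be checked. Layout does not change the derived grade. Listing 21 does show the participant's other chemistry, and clinically significant abnormalities are recorded separately as AEs with investigator-assessed intensity. Both help a careful reader, but neither corrects the grade.

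**Conclusion.** The concern holds. Read as written, SAP 10.6.1 assigns Grade 4 to every direct bilirubin above ULN, never assigns Grade 3, and so contradicts the definitions in its own table. This follows from the text and needs no assumption.

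How often it would appear depends on an exceedance rate that the documents do not give. With 16 participants and assumed rates of 1% to 5%, the chance of at least one false Grade 4 in the listings runs from 15% to 98% across the correlations considered. For Table 2.8 it runs from 0% to 98%. The effect is confined to one analyte in one summary table and two listings. It should be fixed before the outputs are programmed.

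**What to change.** Add an exemption to SAP 10.6.1, for example: direct bilirubin is exempt from the numeric-only and maximum-grade rules; values above ULN are flagged as high without a programmed grade; Grade 3 or 4 is assigned only when the clinical component given in the table is documented. Name the source of that documentation, for instance the AE data already collected, so that the derivation can be reproduced. Make the same change in the programming specification for Table 2.8 and Listings 20 and 21.

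A footnote saying that grades are numeric-only would warn the reader but would leave the wrong grade in place.

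The cost is a short SAP addition and the matching programming change. It needs no new data and has no effect on participants.

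### SAP 10.6.1 prints the SI upper limit for Grade 3 low bicarbonate as 110 mmol/L where its own row implies 11.0, so programming it as printed would misgrade one analyte

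*SAP*

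**What the plan says.** SAP Appendix 6, section 10.6.1, gives the laboratory grading limits in conventional units and, where these apply, again in SI units. For low bicarbonate the units are mEq/L and then mmol/L. The row reads as follows:

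- Grade 1: "16.0 to < LLN 16.0 to < LLN"
- Grade 2: "11.0 to < 16.0 11.0 to < 16.0"
- Grade 3: "8.0 to < 11.0 8.0 to < 110", with a stray point after the last figure
- Grade 4: below 8.0 in both units

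The same section gives three rules for using the table:

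- Source: "Laboratory abnormalities will be graded according to the DAIDS grading table Version 2.1, July 2017".
- Units: "Laboratory results are converted to use SI units; only the numeric part of the criteria will be used".
- Ties: "If for a laboratory parameter there are multiple grades sharing the same criteria, the maximum grade will be used".

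The grades feed Table 2.8 in SAP 10.9.5, titled "Summary of Clinical Chemistry Results by Maximum Grade Increase Post-Baseline Relative to Baseline". They also feed Listings 20 and 21 in SAP 10.9.9, which select chemistry results, and participants, with any toxicity grade. Protocol Appendix 2 (Table 2) includes carbon dioxide in the chemistry panel. It does not list bicarbonate by that name.

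**The concern.** The two halves of the Grade 3 cell disagree, and the half that disagrees is the SI half, on which the SAP says results are graded. A Grade 3 range running up to 110 mmol/L covers the whole of Grade 2, the whole of Grade 1 and any plausible normal value. A participant with normal bicarbonate at baseline would start at Grade 3, so a table built on grade increase would have little room left to show a fall. The toxicity listings would also fill with unremarkable results.

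The grade-based displays for this analyte would then be wrong in two ways: healthy volunteers would be labelled Grade 3, and graded falls would be missed.

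**Working it through.** **Inputs.** The limits are those in the bicarbonate row of SAP 10.6.1. Neither document gives a laboratory normal range for bicarbonate. I assume a lower limit of normal (LLN) of 20, 22 or 24 mmol/L, normal values up to about 30, and a baseline of 26.

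**Step 1: can the printed 110 be reproduced from the row?** The mEq/L to mmol/L factor implied by the other limits is 16.0/16.0 = 1.0, 11.0/11.0 = 1.0 and 8.0/8.0 = 1.0. For the Grade 3 upper limit it is 110/11.0 = 10. Applying the row's own factor gives 11.0 × 1.0 = 11.0. The printed figure is not reproduced.

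**Step 2: do the grades join up?** On the SI line, Grade 4 is below 8.0, Grade 3 is 8.0 to below U, Grade 2 is 11.0 to below 16.0, and Grade 1 is 16.0 to below LLN. The ranges meet without gap or overlap only if U = 11.0. With U = 110, Grade 3 overlaps all of Grades 1 and 2 and extends past LLN.

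**Step 3: grade values with U as printed.** Values of 24, 26, 28 and 30 mmol/L satisfy only the Grade 3 range at all three assumed LLNs. No tie-break is involved. With U = 11.0 the same values carry no grade.

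**Step 4: grade change from a baseline of 26.** The change is the post-baseline grade minus the baseline grade. The baseline grade is 3 as printed and 0 with U = 11.0. Where two grades apply, both resolutions are shown.

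| Fall to (mmol/L) | Grades met as printed | Change, higher grade taken | Change, lower grade taken | Change with U = 11.0 |
|---|---|---|---|---|
| 18 | 1 and 3 | 3 − 3 = 0 | 1 − 3 = −2 | 1 − 0 = +1 |
| 14 | 2 and 3 | 3 − 3 = 0 | 2 − 3 = −1 | 2 − 0 = +2 |
| 10 | 3 | 3 − 3 = 0 | 3 − 3 = 0 | 3 − 0 = +3 |
| 7 | 4 | 4 − 3 = +1 | 4 − 3 = +1 | 4 − 0 = +4 |

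The table is the same for an LLN of 20, 22 or 24. For falls that stay at or above 8.0, no increase appears under either resolution, so the result does not rest on the maximum-grade rule.

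**Step 5: listings.** Any participant with a value from 8.0 to below 110 would have a graded result. In practice that is all of the approximately 16 treated.

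**The case against.** The strongest reply is that this is an evident misplaced decimal that nobody would program. The printed characters are those of 11.0 in another order, the correct figure sits beside them in an equal unit, Grade 2 starts at 11.0, and the SAP names DAIDS v2.1 as its source. The extracted text of this table is also visibly damaged in other rows, so the error may lie in the reading and not on the page. Much of this stands. The intended limit is clear, the harm depends on literal programming, and the printed page should be checked first. But the SAP directs programmers to the SI figures, and the SI figure as we have it is wrong.

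Some stronger readings are tempting but not supported:

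- **Every real fall would be hidden.** It would not: a value below 8.0 still moves from Grade 3 to Grade 4.
- **The maximum-grade rule forces overlapping values to Grade 3.** That rule concerns grades with identical criteria, as with direct bilirubin, where Grades 3 and 4 both reduce to above ULN once the wording is stripped. Extending it to overlapping ranges is an interpretation.
- **The SAP's rules compel the misgrading.** They conflict: the cited DAIDS table governs as well as the SI instruction.
- **The row is certain to be used.** Mapping carbon dioxide to bicarbonate is a strong inference, since no other panel analyte fits the row, but neither document states it.
- **The safety output as a whole conceals the change.** Table 2.7 summarises numeric change regardless of grade, and Protocol 8.2.4 has the investigator review laboratory reports and record clinically relevant changes.

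It can also be argued that the row grades only low abnormalities, so a normal value should never reach it. The SAP states no such screen. If one were applied, a normal baseline would carry no grade. The falls to 18 and 14 would then show +3 if the higher grade were taken, against +1 and +2, and would be graded correctly if the lower were taken. The printed limit would still be unsafe to program.

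**Conclusion.** Wrong as written; minor severity. The Grade 3 SI limit contradicts its own row by a factor of ten. Programmed as printed, normal bicarbonate values meet Grade 3. A fall from normal that stays at or above 8.0 mmol/L shows no grade increase, a fall below 8.0 shows +1 instead of +4, and Listings 20 and 21 include essentially every participant.

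This rests on four assumptions: that the page reads as the extracted text does, that the SI line is coded literally, that normal values are passed through the grading, and that carbon dioxide is mapped to bicarbonate. The reach is one analyte in grade-based descriptive displays. Protocol 9.4.2 plans no formal statistical analysis of safety data, and no PK endpoint, confidence interval or sample-size figure is touched.

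**What to change.** 1. Check the Grade 3 bicarbonate cell on the printed page of the SAP.
2. If it reads as extracted, reconcile the SI limit with the row's mEq/L range (8.0 to <11.0) and with the cited DAIDS v2.1 table.
3. State whether the panel's carbon dioxide result is graded under the bicarbonate row.
4. Before producing Table 2.8 and Listings 20 and 21, check that the conventional and SI limits of each row give the same grade and that adjacent grades do not overlap. Include the triglyceride row: its Grade 3 conventional limit appears as 1.000 while Grade 4 starts above 1,000, which may be another printing or reading slip.

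The cost is one figure, one sentence on mapping and a short programming check. I see no downside.
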